6.6.2 Missing data

Adverse event data

Missing or partial date information for AEs will be replaced according to general Boehringer Ingelheim (BI) rules described in the BI guidance for handling of missing and incomplete AE dates [\(2\)](#).

Adverse event onset dates, including partial onset dates from clinical event committee (CEC):

In the unlikely case that only the year is documented, the day and month will be imputed as 01 Jan unless the subsequently derived date is before randomisation; in this case the date of randomisation will be used as start date.

If year and month is present the day will be imputed as first of the month unless the subsequently derived date is before randomisation; in this case the date of randomisation will be used.

Death date

For patients with a record of death captured on the electronic case report form (eCRF) with missing or only partial death date from all available sources, the death date will be derived as the latest date of any dates as of: event onset and end dates from either the AE page, or CEC adjudicated onset dates, by using also imputed AE dates, last day known to be alive + 1 day and date of trial completion.

Missing information on the date of first administration of trial drug

If the date of first drug administration is missing but the patient was randomised, the date of the first drug administration will be set to the date of randomisation. If the date of first administration is partially missing with the month and year present, the day will be set to the date of randomisation if randomisation was in the same month. If randomisation was in the month prior to the first drug administration the missing day will be imputed as the first day of the month.

Missing date of last FU for non-fatal events.

If the date of last FU for non-fatal events is missing, it will be imputed as the last of any of the following data:

- visit dates
- date if any assessment such as NYHA, blood pressure, EQ5D, KCCQ, pregnancy test, central laboratory
- adverse event/outcome event start and end dates except fatal events
- onset dates of adjudicated (confirmed and non-confirmed) events except fatal events
- drug administration dates, last drug stop date,
- date of clinical routine exam
- date of trial completion (if patient did not die)

Missing date of trial completion (=last contact or date of death)

If the date is completely missing the following rules will be applied:

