- If a patient has withdrawn informed consent, this date will be imputed by the date of IC withdrawal.
- If a patient died and has not withdrawn consent, this date will be imputed by the date of death.
- If the date is incomplete with only month and year reported, the date will be imputed by the first day of the month.
- If a patient did not die, the date of trial completion will be imputed by the last date the patient was known to free of non-fatal events.

All other cases need to be assessed by the trial team on an individual basis, using the above points as guidance.

Missing information on the date of trial medication stop

- If this date is missing and the end-of treatment visit date is available, date of trial medication stop will be imputed by the date of the end-of-treatment visit.
- If the date is incomplete with only month and year and the respective visit date is missing, the date of last drug administration will be imputed by the last day of this month. If this would be later than the date of trial completion, then the date of trial completion will be used for imputation.
- If a patient is lost-to-follow up, no date of last drug administration is reported and the date of the end-of treatment visit is not available, the date of last drug administration is set as the date of last FU for non-fatal events.
- For a patient who dies in the treatment phase with no information on the date of last drug administration, the date is set as the date of death, assuming that the patient took the medication until the date of death.

If the imputed date based on the above rules is later than the longest treatment duration based on drug supply, then trial medication stop will be imputed based on the longest treatment duration based on drug supply.

If after imputation, the date of trial completion is before the date of last drug administration, the start of the post-study period is defined as the maximum of last drug administration +1 day and the date of the trial completion +1 day.

All other cases need to be assessed by the trial team on an individual basis, trying to use the points above as guidance.

Missing information on concomitant therapy dates

For incomplete date information always the midpoint of the possible interval will be used. If only the year is present the day and month will be imputed as 01 July, if year and month is present the day will be imputed as 15. If the year is missing, the date will be considered missing.

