6.6.2 Missing data

Adverse event data

Missing or partial date information for AEs will be replaced according to general Boehringer Ingelheim (BI) rules described in the BI guidance for handling of missing and incomplete AE dates (2).

Partial onset dates from clinical event committee (CEC):

In the unlikely case that only the year is documented, the day and month will be imputed as 01 Jan unless the subsequently derived date is before randomisation; in this case the date of randomisation will be used as start date.

If year and month is present the day will be imputed as first of the month unless the subsequently derived date is before randomisation; in this case the date of randomisation will be used.

Death date

For patients with a record of death captured on the electronic case report form (eCRF) with missing or only partial death date from all available sources, the death date will be derived as the latest date of any dates as of: event onset and end dates from either the AE page, or CEC adjudicated onset dates, by using also imputed AE dates, last day known to be alive + 1 day, range of possible days based on partial death date and date of trial completion.

Missing information on the date of first administration of trial drug

If the date of first drug administration is missing but the patient was randomised, the date of the first drug administration will be set to the date of randomisation. If the date of first administration is partially missing with the month and year present, the day will be set to the date of randomisation if randomisation was in the same month. If randomisation was in the month prior to the first drug administration the missing day will be imputed as the first day of the month.

Missing date of trial completion (=last contact or date of death)

If the date is completely missing the following rules will be applied:

- If a patient has withdrawn informed consent, this date will be imputed by the date of IC withdrawal.
- If a patient died and has not withdrawn consent and is not lost to follow-up, this date will be imputed by the date of death.
- If a patient did not die, the date of trial completion will be imputed by the last date the patient was known to free of non-fatal events. This is defined as the maximum of
 - the last date the patient could be followed up for all non-fatal events as documented in the eCRF
 - last onset or end date of an AE
 - Onset of an adjudicated event
 - End of treatment

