 - last visit date (NYHA class, EQ-5D, KCCQ, pregnancy test, vital signs, ECG, or central laboratory reported)

In case of a partially missing date, if the imputed date is before the first day (after the last day) of the month/year given as partial date, the first day (last day) of the month/year will be used.

All other cases need to be assessed by the trial team on an individual patient basis, using the above points as guidance.

Missing information on the date of trial medication stop

If the date is partially or completely missing, use the minimum of the following dates:

- End of treatment visit date if available
- Date of death
- Trial completion (last contact date)
- Longest extrapolated treatment duration (assuming 1 tablet/day)
- (in case for partially missing date) Last day of the year/month given as partial date

In case of a partially missing date, if the imputed date is before the first day of the month/year given as partial date, the first day of the month/year will be used.

All other cases need to be assessed by the trial team on an individual patient basis, using the points above as guidance.

Missing information on concomitant therapy dates

For incomplete date information generally the midpoint of the possible interval will be used. If only the year is present the day and month will be imputed as 01 July, if year and month is present the day will be imputed as 15. If the year is missing, the date will be considered missing.

If this leads to contradictions for the start or end date of a concomitant therapy (e.g. imputed end date before documented start date) a partial end date will be imputed as the end of the interval or a partial start date will be imputed as the start of the interval in the database to resolve this contradiction.

If the medication is reported as being taken at visit 2 (baseline) and the imputed start/end date contradicts this then the start/end date is imputed to the earliest/latest date respectively if this can resolve the contradiction.

Similarly if the medication is reported as not taken at visit 2 (baseline) and the imputed start/end date contradicts this then the start/end date is imputed to the baseline date/ 1 day prior to baseline respectively if this can resolve the contradiction.

All other cases or conflicting cases resulting from these imputation rules need to be assessed by the trial team on an individual patient basis.

Missing measurement to confirm “sustained” decrease

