An eGFR (CDK-EPI)_{cr} reduction is considered sustained, if it is determined by two or more consecutive post-baseline central laboratory measurements separated by at least 30 days (first to last of the consecutive eGFR values). If there is no additional measurement \geq 30 days after the eGFR reduction is observed and the patient dies within 60 days of this measurement, then the eGFR reduction is also considered sustained.

Pharmacokinetic (PK) variables

Missing data and outliers of PK data are handled according to [\(3\)](#)

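### The current death-date rule has no upper bound, so a death known to the month or year can be dated after that month or year (minor wording correction)

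*SAP*

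**What the plan says.** The file holds two versions of the SAP: the first, of February 2017, and the revision of February 2021, which governs. In both, the Death date rule in Section 6.6.2 applies to a recorded death "with missing or only partial death date from all available sources", and in both "the death date will be derived as the latest date of any dates as of: event onset and end dates". The candidates include adverse-event onset and end dates (imputed ones too) and onset dates from the adjudication committee.

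The versions differ in the rest of the list. The 2017 text ends with "by using also imputed AE dates, last day known to be alive + 1 day and date of trial completion" and makes no use of a known month or year of death. The current text ends with "last day known to be alive + 1 day, range of possible days based on partial death date and date of trial completion".

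Two neighbouring rules in the current Section 6.6.2 treat partial dates differently. For trial completion, the text says "In case of a partially missing date, if the imputed date is before the first day (after the last day) of the month/year" of the partial date, then the first (or last) day of that period is used. For the trial-medication stop date, the rule takes a minimum that includes the last day of the known month or year, and it sets the first day as a floor.

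**The concern.** A range of possible days limits a date only if the rule says so. Placed inside a latest-of list, it works as a floor and not as a ceiling. Any later candidate overrides it, even when the partial date shows that candidate cannot be the day of death.

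The date of trial completion is one such candidate, because the SAP heads that item "Missing date of trial completion (=last contact or date of death" and so allows it to be a contact date. The end date of another adverse event is a second.

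Section 6.8.2 makes the date of death the event date for CV death, all-cause mortality and the death component of the primary composite. The same date also feeds several rules with a boundary:

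- confirmation of an eGFR decline when "the patient dies within 60 days of this measurement, then the eGFR reduction is also considered sustained" (Section 6.6.2);
- analyses censored at treatment stop + 30 days (Section 6.8.3);
- KCCQ scores of 0 at scheduled visits after death (Section 6.6.1);
- the COVID-19 cut-off dates (Sections 7.4.2 and 7.5.1) and the interim cut-off (Section 9.5).

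A death dated too late can fall on the wrong side of any of these.

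**Working it through.** The SAP gives no figure to reproduce here, so the check applies the rule to test cases. The dates are assumed; only the rule comes from the SAP.

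**Rules compared**

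- 2017 text: D = max(AE dates, adjudicated onset dates, last alive + 1, trial completion).
- Current text: D = max(the same list, a day from the partial-date range). The SAP does not say which day of the range enters, so both ends were tried.
- Bounded rule: min(max(D from the 2017 list, first possible day), last possible day).

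**Cases: death known only as June 2019 (possible days 1 to 30 June)**

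| Case | 2017 text | Current text | Bounded rule |
|---|---|---|---|
| A: last alive 10 April, AE onset 20 April, completion 10 April | 20 April (too early) | 1 June or 30 June, by end of range used | 1 June |
| B: last alive 20 May, AE onset 1 June, completion (last contact) 15 August | 15 August (too late) | 15 August (too late) | 30 June |
| C: last alive 20 May, AE onset 1 June, another AE ending 31 July, completion 1 June | 31 July (too late) | 31 July (too late) | 30 June |

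Case A shows that the current text cures dates that are too early. Cases B and C show that dates that are too late remain, whichever end of the range is used.

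**Size of the shift in case B**

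- From 30 June to 15 August: 31 + 15 = 46 days.
- From 1 June to 15 August: 29 + 31 + 15 = 75 days.

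**Consequences for single patients**

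- Sustained eGFR rule, unconfirmed decline on 28 May. Any June death is at most 3 + 30 = 33 days later, so the decline counts as sustained. The derived date is 3 + 30 + 31 + 15 = 79 days later, beyond 60, so it does not count.
- Treatment stop + 30 days, drug stopped on 10 June. A death later in June is at most 20 days after the stop and is counted. The derived date is 20 + 31 + 15 = 66 days after it, so the patient is censored at day 30.
- COVID-19 cut-off, 31 December 2019 outside China. A death known as December 2019 but dated to a January 2020 contact drops out of the pre-outbreak analysis.
- KCCQ. A scheduled visit between the true and the derived date does not receive the score of 0.

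**Scale for the primary endpoint**

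The event target in Section 9.6 is 841. One misdated death is 1/841 = 0.12% of events. In the primary analysis it would generally be moved in time and not lost. If an adjudicated HHF came first, the composite event time does not change at all.

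**The case against.** The best defence is that a range is not a date and cannot sensibly enter a maximum, so it must be meant to limit the admissible days. That may be the intent. But the stated operator is the latest of the list, nothing says the range overrides later entries, and the same section writes such a limit out in full for trial completion. A programmer following the text would not apply a cap.

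The defence is right on several other points, and they limit the finding:

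- One full date of death in any source switches the rule off.
- Harm also needs a later full contact or adverse-event date. The SAP does not say that a relative's report of a death is entered as last contact. Whether imputed adverse-event end dates can run past death depends on a sponsor guidance that is cited but not shown.
- For a patient who died, did not withdraw consent and was not lost to follow-up, a completely missing completion date is set to the date of death, so that route adds no overshoot.
- If contact was lost before death, the last-contact date is early and has no effect in a maximum.

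Three stronger readings are tempting, and the SAP does not support them. First, a reader might infer that deaths can be dated on either side of the known period. That was true of the 2017 text, which is superseded; in the current text only the late side is open. Second, a reader might infer that the dependent rules fail. They still run, and at worst they misclassify single patients. Third, a reader might infer a material or directional bias in the primary hazard ratio. The rule does not use treatment assignment, and no count of partial death dates is given from which an effect could be derived.

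**Conclusion.** The point holds as a minor correction to the current Section 6.6.2. Followed literally, the rule can give a primary-endpoint event a date that the trial's own partial date rules out, and only in the late direction. The 2017 wording matters only as history.

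The shift of 46 to 75 days belongs to the assumed June and August dates and is not an estimate for this trial. That few deaths are affected is a judgement from how narrow the conditions are: no full date anywhere, plus a later competing date. On that basis the effect on the primary hazard ratio is negligible. What remains is possible misclassification of single patients in the date of CV death and in the boundary rules. Deaths with no date information at all are outside this point, since there is no known period to bound them to.

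**What to change.** In the Death date paragraph of the current Section 6.6.2, replace the range item in the list with a sentence such as: if a partial death date exists and the derived date falls before the first or after the last day of the known month or year, that first or last day is used; the day after the patient was last known alive is the lower limit within that period. This mirrors the trial-completion rule and also settles which day of the range applies, which the current text leaves open (case A). A patient recorded as alive after the known period is a data conflict, to be queried and not imputed.

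The cost is one sentence and a small change to the derivation program. No new data are needed. A one-line count of deaths with an imputed date, by treatment group, would let readers confirm that the effect is negligible.

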6.7 BASELINE, TIME WINDOWS AND CALCULATED VISITS

For serum creatinine and values based on upon this measurement such as eGFR, baseline will be defined as the mean of all available measurements from the screening visit until start of randomised trial medication. For all other endpoints, baseline will be defined as the last available measurement before start of randomised trial medication.

Since the protocol specifies, that all measurements are taken at visit 2 before any intake of trial medication, all measurements at the first day of drug intake are analysed as before any intake of randomised trial medication.

For randomised patients without any treatment intake: For serum creatinine and values based on upon this measurement such as eGFR, baseline will be defined as the mean of all available measurements from the screening visit until and including the day of randomisation. For all other endpoints, baseline will be defined as the last available measurement before or on the day of randomisation.

Measurements taken after the first intake of randomised trial medication will be considered on-treatment values if they have been obtained up to end of the parameter specific follow-up period as defined in [Table 6.7: 1](#) below and will be assigned to the randomised study drug for efficacy and safety analyses.

Measurements taken after the end of the endpoint specific follow-up period and after the last intake of study drug will be considered post-treatment values.

On-treatment (for OC-OT analysis) or all post-randomisation (for OC-AD analysis) efficacy and safety measurements will be assigned to visits based on time windows around the planned visit dates. These time windows are defined based on the planned number of days after the date of first administration of study drug.

The time window for the first visit after randomisation starts on the day after the first intake of study drug. The midpoint between two on-treatment visits defines the end of a time window, with the midpoint being included in the time window of the preceding visit.

Table 6.7: 1 Time windows for post-baseline efficacy measurements scheduled for each on-treatment visit for the first 3 years

Visit number	Visit label	Planned days	Time window (actual days after baseline)	
			Start	End
Endpoints assessed at each on-site visit (e.g. creatinine / eGFR)				
2	Baseline	0	NA	1
3	Week 4	28	2	56
4	Week 12	84	57	154
6	Week 32	224	155	294
8	Week 52	364	295	448
10	Week 76	532	449	616
12	Week 100	700	617	784
14	Week 124	868	785	952
16	Week 148	1036	953	1120
18	...			
FU	FU	Trt stop + 30 days	Trt stop + 23 days	Trt stop + 45 days
KCCQ				
2	Baseline	0	NA	1
3	Week 4	28	2	126
6	Week 32	224	127	294
8	Week 52	364	295	532
FU	FU	Trt stop + 30 days	Trt stop + 23 days	Trt stop + 45 days

^A Only values taken prior to the start of treatment with randomised study drug can be considered baseline values. Time windows will be used for assignment of measurements to scheduled visits.

For examinations that are not planned at every on-treatment visit, the time windows will be defined according to the same algorithm, based on the midpoint between the planned visit day of such an examination. Examples for eGFR and KCCQ can be found in [Table 6.7: 1](#)

Only one observation per time window will be selected for analysis at an on-treatment visit – the value will be selected which is closest to the protocol planned visit day. If there are two observations which have the same difference in days to the planned day or if there are two observations on the same day, the first value will be used.

Time windows for assignment of planned off-treatment measurement

For evaluation of the off-treatment assessment 'at 30 day follow-up' only values obtained at ≥ 23 days to ≤ 45 days after last trial drug stop will be considered.

The value that is closest to the planned day of 30 days after last trial drug stop will be used. If there are 2 values equally close, the later value will be used.

6.8 CALCULATION OF TIME TO EVENT

This section describes the calculation of the time to event and the time that patients without an event are in the study (under risk).

Consistent with that approach, the respective time intervals determine the start and end for the derivation of occurrence of a specific event.

For those patients with an event, the time to event is calculated as:

$\langle \text{date of event} \rangle - \langle \text{start date} \rangle + 1$

For those patients without an event, the time at risk is calculated as:

$\langle \text{date of censoring} \rangle - \langle \text{start date} \rangle + 1$

6.8.1 Start date

In general, the time to event will be derived from the date of randomisation.

If study drug administration happened before calling IVRS, the date of first drug administration will be used as start date.

For the following endpoints (analysed as occurrence or time to first event), the date of first drug intake will be used as start date:

- AE analyses acc. to [Section 7.8.1](#)
- Endpoints purely based on laboratory measurements, that include a relation to baseline (such as change decrease from baseline $\geq 40\%$, doubling vs baseline, etc.)

Please note, that for composite endpoints, that include component(s) using randomisation date and other component(s) using first drug intake date as start date, the time at risk for the composite will start with date of randomisation (which may be earlier). For the individual components, the component specific start date will be used.

